6.1 Analyses for SMC meetings

Details of analyses for SMC meetings are specified in a separate IAP, provided in [Appendix 18.1](#).

7 Changes to the Planned Analyses in the Clinical Study Protocol

The study was stopped due to lack of enrollment before part B was started and before part A reached its primary objective. Therefore, additional to the SMC analyses there is only one primary analysis (this includes the end of dose escalation analysis).

There is one change in the definition of the DLT analysis set compared to the protocol. The following is added:

“Additionally, participants that did not receive at least 80% of the planned total dose of study treatment, but at least 80% dosing of a different (lower) dose level, did not miss more than 20% of planned administrations, and finished the DLT period are eligible for the DLT analysis set to be analyzed in the highest dose level they received 80% of dosing.”

The protocol only mentioned β 5c as an endpoint for part B, however, data analyses for this marker are planned for the dose escalation part A, too.

In case the received cumulative dose is higher than planned dose (and all other criteria for inclusion in DLT analysis set are fulfilled) the participant will still be analyzed in the planned dose level. For analysis of pharmacodynamic markers and efficacy analysis the participant will be shown in listings and figures showing data on individual level. A footnote will explain the cumulative dosing the subject received. In summary analysis of pharmacodynamic markers and efficacy analysis the participant’s data will not be included.

8 Analysis Populations and Subgroups

8.1 Definition of Analysis Populations

The analysis populations are specified below. The final decision to exclude participants from any analysis population will be made during a data review meeting prior to database lock except for the DLT analysis populations. For the DLT analysis populations, decisions for DLTs are taken by the SMC.

Screening Analysis Population (SCR)

The Screening analysis population includes all participants who signed the informed consent.

Safety Analysis Population (SAF)

The Safety analysis set will include all participants who were administered any dose of any study intervention. Analyses will consider participants as treated, meaning that participants will be classified according to the study intervention actually received (regarding dose level, see [section 9 General Specifications for Data Analyses including](#) explanation on how to deal with participants that did receive a dose different to the planned dose).

Dose Limiting Toxicity Analysis Population (DLT)

The Dose Limiting Toxicity analysis population (DLT) will include all participants who received at least one dose of study intervention and meet at least one of the following criteria:

- Experienced at least one DLT during the DLT period, regardless of the administered number of doses of study intervention/completion of the DLT period
- Received at least 80% of the planned cumulative dose and at least 80% of planned administrations (eg.: 4 administrations by cycle, 2 administrations by week...etc.) of each treatment during the DLT period and completed the DLT period.
- Additionally, participants that did not receive at least 80% of the planned total dose of study treatment, but at least 80% dosing of a different (lower) dose level, did not miss more than 20% of dosing, and finished the DLT period are eligible for the DLT analysis set to be analyzed in the highest dose level they received 80% of dosing of.

In case the received cumulative dose is higher than planned dose (and all other criteria for inclusion in DLT analysis set are fulfilled) the participant will still be analyzed in the planned dose level

Pharmacokinetics Population (PK)

The pharmacokinetics population (PK) will include all participants, who received at least one dose of study intervention, have no clinically important protocol deviations or important events affecting PK, and provide at least one measurable postdose concentration. Participants will be analyzed per the actual study intervention they received.

Pharmacodynamics Population (Pd)

The pharmacodynamics population (Pd) will include all, who received at least one dose of study intervention, have no clinically important protocol deviations or important events affecting Pd, and provide at least one measurable Pd endpoint postdose. In case the received cumulative dose of a participant is higher than the planned dose, the participant's data will be included in listings and figures showing data on individual level. A footnote will explain the cumulative dose the subject received. In summary analysis of pharmacodynamic markers the participant's data will not be included.

Analyses per Analysis Population

The following table summarizes the use of the analysis sets in the different analyses.

Analyses	Analysis Population			
	SAF	DLT	PK	Pd
DLT		✓		
Safety and Tolerability	✓			
PK			✓	
Pd				✓
Efficacy	✓			
Exploratory biomarkers (MRD)	✓			
Baseline Characteristics	✓			
Previous and Concomitant Therapies	✓			
Compliance and Exposure	✓			

Note:

Safety, PK, will be described by actual dose.

Baseline characteristics and compliance and exposure will be described for both (by planned dose and actual dose) if different.

All other analyses will be described by planned dose, according to Intention To Treat principle.

For more details see [section 9 General Specifications for Data Analyses including](#).

9 General Specifications for Data Analyses

This section describes any general specifications not included in subsequent sections.

Study intervention is defined and labelled as "M3258".

Analyses will be displayed separately by regimen (ordered by dose intensity starting from most intensive regimen (QD)), dose (in increasing order and not evaluable at the final) and summarized.

The planned regimen and dose level will be taken from the CRF "Cohort Assignment".

General rule for actual dose if actual dose differs from planned dose (determined during the DLT period):

- Planned dose > dose received
- If the participant receives at least 80% of his cumulative planned dose or has DLT during DLT period, then his actual dose will be his planned dose

- If the participant receives less than 80% of his cumulative planned dose and has no DLT during DLT period but received at least 80% of a cumulative lower tested dose, then his actual dose will be the lower dose level he received at least 80% of cumulative dose for safety analyses and the planned dose is used for all other analyses.
- If the participant receives less than 80% of the cumulative of any tested dose or less than 80% of the planned administrations or did not finish the DLT period the participant is not evaluable for the DLT analysis set (this category will be presented in the tables for DLT analysis set), but for other safety analyses. For other safety analyses in this case the participant will be analyzed with the
 - planned dose in case he did receive less than 80% cumulative dose of any tested dose
 - Cumulative dose he received 80% of (in case he missed too many dosings or did not finish the DLT period)
- Planned dose < dose received:
 - Actual dose will be the planned dose (in DLT analysis set)
 - For analysis of pharmacodynamic markers and efficacy analysis the data of such a participant will be shown in listings and figures showing data on individual level. A footnote will explain the cumulative dosing the subject received. In summary analysis of pharmacodynamic markers and efficacy analysis the data of such a participant will not be included.

The “start date” for this study is the date of first study drug administration (M3258).

All analyses will be performed using SAS® Software version 9.2 or higher, and otherwise as specified (e.g. for Bayes modeling)

Significance level:

There is no formal significance level for this study, and all analyses are considered descriptive.

There will be no statistical tests performed. If confidence or credibility intervals are mentioned, the level will be 95% unless otherwise specified.

Presentation of continuous and qualitative variables:

Continuous variables will be summarized using descriptive statistics, i.e.

- number of participants with non-missing values (n)
- mean, standard deviation (SD)

- median, 25th Percentile - 75th Percentile (Q1-Q3)
- minimum, maximum

If there are fewer than 5 observations summarized, only the number of participants with non-missing values, the mean, and the minimum and maximum will be given.

Qualitative variables will be summarized by counts and percentages.

Unless otherwise stated the calculation of proportions will be based on the number of participants in the analysis set of interest. Therefore, counts of missing observations will be included in the denominator and presented as a separate category.

Deviations from this definition might apply to the PK analysis (see section 16.1 for definitions).

Descriptive statistics will be computed by treatment day (C1D1, C1D2, C1D8, ..., EOT). Unscheduled visits will be included in the derivation of baseline (if occurred within the allowed screening period) or worst on-treatment values and in any analysis using treatment day (e.g. plots of lab data).

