6.6 Dose Selection and Modification

Dose escalation will proceed according to the SMC recommendation until the 50 mg dose level or the MTD is reached (whichever is lower). For further dose cohorts, a SMC will meet and review all available data to provide recommendations on the next dose level. In case escalation should proceed to doses higher than 50 mg, a protocol amendment will be submitted. Details are described in the SMC charter. The SMC receives outputs of a Bayesian dose-toxicity model estimated DLT probabilities for potential next dose levels. The Bayesian model will be based on prior, observed number of evaluable participants and number of participants with DLT. Further details on the Bayesian model are provided in Section 9.4.2. Further details on the SMC are provided in Section 10.

A DLT is defined as any of the AEs listed below as assessed by the Investigator and/or the Sponsor at any dose and regimen, and judged not to be related to the underlying disease or any previous or concomitant medication or concurrent condition occurring during the DLT observation period (first treatment cycle), according to the NCI-CTCAE v 5.0. Any DLT must be confirmed by the SMC.

During the DLT assessment period: Treatment with transfusions or growth factors (e.g., G-CSF, erythropoietin) is not permitted. Transfusions are only permitted if clearly related to multiple myeloma.

Participants who develop a DLT will permanently discontinue treatment.

Participants who did not receive $\geq 80\%$ of the planned cumulative dose or missed more than 20% of doses in the DLT period will not be considered in the DLT analysis set unless they experienced a DLT.

AEs judged as DLT will include:

- Any Grade ≥ 3 nonhematologic AE with exception of:
 - Single laboratory values out of abnormal range that have no clinical correlate, and resolve to Grade ≤ 1 or to Baseline within 7 days with adequate medical management
 - Grade 3 diarrhea persisting ≤ 72 hours after initiation of medical management
 - Nausea and vomiting of ≤ 72 h duration with adequate and optimal therapy
 - Transient (< 1 week) Grade 3 fatigue, local reactions, flu-like symptoms, fever, and headache (≤ 72 h) that resolves to Grade ≤ 1 with adequate treatment
 - Grade 3 nonrecurrent skin toxicity that resolves to Grade ≤ 1 in less than 7 days after initiation of medical management
 - Asymptomatic Grade ≥ 3 lipase or amylase elevation not associated with clinical manifestations of pancreatitis.

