9.6 Study Day / Study Treatment Day definition

Treatment day is defined relative to the date of first study drug administration (M3258). Treatment Day 1 is treatment start date of first administration of the study drug; the day before is defined as Treatment Day -1 (no Treatment Day 0 is defined).

10**Study Participants**

The subsections in this section include specifications for reporting participant disposition and study intervention/study discontinuations. Additionally, procedures for reporting protocol deviations are provided.

10.1**Disposition of Participants and Discontinuations**

A table will display the following (per regimen and dose level and overall):

- Number of participants in each analysis population (SCR, SAF, DLT, PK, Pd)
- Number of participants who discontinued from the study prior to treatment overall and grouped by the main reason (participants did not meet eligibility criteria, withdrew consent, other)

This table will be produced twice if there are participants with differing planned dose and actual dose, one by planned dose (including SCR, SAF, Pd, PK) and one by actual dose (including SCR, SAF, DLT, PK).

This table will additionally be displayed by site.

Another table of disposition will provide the following, among participants in SAF:

- Number and percentage of participants still in trial
- Number and percentage of participants withdrawn from trial
- Number of participants by reason for withdrawal

Additionally a listing will display all discontinued patients including planned regimen and dose, the reason for discontinuation from treatment and reason for discontinuation from study and treatment start and end date.

10.2**Protocol Deviations / Exclusion from Analysis Population****10.2.1****Important Protocol Deviations**

Important protocol deviations (IPDs) are protocol deviations that might significantly affect the completeness, accuracy, and/or reliability of the study data or that might significantly affect a participant's rights, safety, or well-being.

The IPDs will be identified for all participants by either site monitoring, medical review processes or programming and confirmed prior to or at the Data Review Meeting at the latest.

All important protocol deviations are documented in SDTM datasets whether identified through site monitoring, medical review or programming.

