16.1 Pharmacokinetics

16.1.1 Pharmacokinetic Analysis

Pharmacokinetic parameters for M3258 in Plasma will be calculated by Covance, using standard non-compartmental methods and the actual administered dose. PK parameters will be calculated using the actual elapsed time since dosing. In cases where the actual sampling time is missing, calculations will be performed using the scheduled time.

Non-compartmental computation of pharmacokinetic parameters will be performed using the computer program Phoenix® WinNonlin® version 6.4, or higher (Certara, L.P., [name]).

The following PK parameters will be calculated, where applicable:

Parameter	Definition
-----------	------------

$AUC_{extra\%}$	percentage of AUC that is due to extrapolation from the last measurable concentration to infinity(single dose only)
AUC_{0-t}	area under the concentration-time curve from time 0 to the time of last quantifiable concentration (t_{last}) (single dose only)
AUC_{0-8}	area under the concentration-time curve from time 0 to 8h postdose
t_{lag}	time immediately prior to the first quantifiable concentration
C_{max}	maximum observed plasma concentration
t_{max}	time of maximum observed plasma concentration
t_{last}	time of last quantifiable plasma concentration
C_{trough}	The concentration observed immediately before next dosing (corresponding to predose or trough concentration for multiple dosing)
$t_{1/2}$	apparent plasma terminal elimination half-life
λ_z	apparent terminal elimination rate constant
$Racc_{(C_{max})}$	accumulation ratio based upon C_{max} (M3258 multiple dose only)
$Racc_{AUC0-8}$	accumulation ratio based upon AUC_{0-8} (M3258 multiple dose only)

Additional parameters may be calculated where appropriate

Dose normalized parameters, C_{max}/D , AUC_{0-t}/D , and AUC_{0-8}/D , will be calculated by dividing the original parameter by dose in mg.

C_{max} and t_{max} will be obtained directly from the plasma concentration-time profiles.

For multiple peaks, the highest postdose concentration will be reported as C_{max} . In the case that multiple peaks are of equal magnitude, the earliest T_{max} will be reported.

Accumulation ratios will be determined from single dose and multiple dose (at steady state) C_{max} , and $AUC_{0-8\tau}$ as follows

$$R_{acc(C_{max})} = \frac{C_{max, \text{multiple dose}}}{C_{max, \text{single dose}}}$$

$$R_{accAUC_{0-8}} = \frac{AUC_{0-8, \text{multiple dose}}}{AUC_{0-8, \text{single dose}}}$$

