16.1.2 Presentation of Pharmacokinetic Data

Available individual M3258 plasma concentrations will be listed and summarized by regimen, dose, study day, analyte and scheduled collection time, including summary statistics where data allows, using: number of non-missing observations (N), arithmetic mean (Mean), standard deviation (SD), coefficient of variation (CV%), minimum (Min), median (Median) and maximum

(Max). Pharmacokinetic parameters will be summarized additionally, using the geometric mean (GeoMean), the geometric coefficient of variation (GeoCV) and the two-sided 95% confidence interval for the GeoMean (LCI 95% GM, UCI 95% GM). For time to reach maximum observed concentration (t_{max}), only n, Min, Median, and Max will be reported.

Descriptive statistics of PK concentration data will be calculated using values with the same precision as the source data and rounded for reporting purposes only. Descriptive statistics will only be calculated for $N > 2$ in which a measurement of <LLOQ represents a valid measurement.

Descriptive statistics will be calculated for pharmacokinetic parameter where $N > 2$. All no result (NR) and not done (nd) values will be set to missing.

PK parameters read directly from the measurements (i.e. C_{max}) will be reported with the same precision as the source data. All other PK parameters will be reported to 3 significant figures.

The following conventions will be applied when reporting descriptive statistics of PK data:

Mean, Min, Median, Max, GeoMean, two-sided 95% CI: 3 significant digits

SD 4 significant digits

CV%, GeoCV%: 1 decimal place

Individual M3258 plasma concentrations will be plotted by study day, analyte and scheduled collection time, including summary statistics where data allows.

Both individual and arithmetic mean concentration-time profiles, will be plotted on linear and semi-logarithmic scales as follows:

- Spaghetti plots showing M3258 plasma concentration vs actual time all individuals per regimen and dose group; Day1 Cycle 1 and Day 15 Cycle 1
- Individual per participant plots showing M3258 overlaying Day 1 Cycle 1 and Day 15, Cycle 1 concentration profiles
- Arithmetic mean concentration-time profile showing M3258 per regimen and dose group with Day 1, Cycle 1 and Day 15, Cycle 1 overlaid. On linear plots $\pm SD$ will be included.
- Arithmetic mean concentration-time profiles per Day, overlaying Single and Multiple Dose Day 1 and Day 15. On linear plots $\pm SD$ will be included.

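### The SAP groups PK by actual dose in section 8.1 and by planned dose in section 9, and neither rule always matches the dose behind a profile

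*SAP*

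**What the plan says.** Five places in the SAP bear on which dose labels a PK result.

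- **SAP 8.1**, in the note under the table of analyses by population: "Safety, PK, will be described by actual dose". It refers to section 9 for details. The PK population definition adds that participants are analysed by the intervention they really received, but does not turn that into a dose level.
- **SAP 9** introduces its rule as "General rule for actual dose if actual dose differs from planned dose (determined during the DLT period"). A participant with at least 80% of the planned cumulative dose, or with a DLT, keeps the planned dose. One below that, but with at least 80% of a lower tested cumulative dose, takes the lower level "for safety analyses and the planned dose is used for all other analyses".
- **SAP 10.1** produces the disposition table twice when the doses differ: "one by planned dose (including SCR, SAF, Pd, PK) and one by actual dose (including SCR, SAF, DLT, PK").
- **SAP 16.1.2**: "plasma concentrations will be listed and summarized by regimen, dose, study day". It does not say which dose.
- **SAP 16.1.1** calculates parameters "using standard non-compartmental methods and the actual administered dose". This governs the calculation, not the grouping.

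Protocol 6.6 fixes the window: a DLT is an event "occurring during the DLT observation period (first treatment cycle"), so actual dose depends on the whole of Cycle 1.

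**The concern.** PK is not a safety analysis, so SAP 8.1 and SAP 9 give different groups for the same participant, and sections 10.1 and 16.1.2 do not settle which applies.

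Neither label is built for PK. A profile reflects the dose taken that day and the doses before it. Reductions later in Cycle 1 cannot change an exposure already measured, yet they can change the actual dose of section 9. Planned dose has the opposite fault: it ignores a reduction made before the profile.

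Cmax and AUC of M3258 are secondary endpoints of Part A (Protocol section 3), and the planned cohort size is 3 (Protocol 9.2). One misplaced profile can therefore visibly shift a dose-level mean.

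**Working it through.** The plan gives no figure to reproduce here. The check applies the section 9 rule to each regimen in Protocol 4.1.

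**Inputs.** Dose levels: SAP 14.2 names 10 mg and 20 mg twice weekly (BIW), so a move from 20 to 10 mg within one regimen is possible. Individual reductions are permitted at any time except in the first cohort (Protocol 6.6). The multiple-dose PK day is Day 8 in the protocol (Table 5) and Day 15 in the SAP plots (16.1.2).

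**Rule.** With n administrations in Cycle 1, the planned total is 20n mg at 20 mg and 10n mg at 10 mg. A participant without a DLT, with no missed dose and with the DLT period completed, becomes 10 mg if 0.8 × 10n ≤ received < 0.8 × 20n. With k doses at 20 mg and the rest at 10 mg, received = 20k + 10(n − k).

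**Reduction to 10 mg straight after the Day 8 dose:**

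| Regimen | n | 80% of 20 mg total | 80% of 10 mg total | Received (share of planned) | Level |
|---|---|---|---|---|---|
| BIW, 28-day | 8 | 128 | 64 | 3×20 + 5×10 = 110 (68.75%) | 10 mg |
| BIW, 21-day | 4 | 64 | 32 | 3×20 + 1×10 = 70 (87.5%) | 20 mg |
| QD, 28-day | 28 | 448 | 224 | 8×20 + 20×10 = 360 (64.3%) | 10 mg |
| QD Days 1–14 of 21 | 14 | 224 | 112 | 8×20 + 6×10 = 220 (78.6%) | 10 mg |

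In three of the four regimens the Day 1 and Day 8 profiles, both taken at 20 mg, carry the label 10 mg if SAP 8.1 is followed. On BIW 21-day, a reduction after Day 4 gives 2×20 + 2×10 = 60 mg (75%), so there the Day 1 profile is misplaced.

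**If the multiple-dose day is Day 15.** BIW 28-day with reduction after Day 15: 5×20 + 3×10 = 130 mg (81.25%), so the label stays 20 mg. QD 28-day: 15×20 + 13×10 = 430 mg (76.8%), so the label is 10 mg.

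**Both rules on one participant.** BIW 28-day, 20 mg on Days 1 and 4, then 10 mg from Day 8: 2×20 + 6×10 = 100 mg, again between 64 and 128. SAP 8.1 labels both profiles 10 mg, which is wrong for Day 1. SAP 9 labels both 20 mg, which is wrong for Day 8.

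**Size.** Assume dose-proportional exposure and set a 10 mg exposure to 1 and a 20 mg exposure to 2. One misplaced 20 mg profile then gives these 10 mg means:

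- with two true 10 mg participants: (1+1+2)/3 = 1.33, or +33% (geometric 2^(1/3) = 1.26, +26%);
- with three: (1+1+1+2)/4 = 1.25, or +25% (geometric 2^(1/4) = 1.19, +19%).

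SAP 16.1.2 calculates PK statistics only for N > 2. Moving one participant out of a 20 mg cohort of three leaves 3 − 1 = 2, so that group loses its summary.

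**The case against.** The best reply is that section 9 expressly keeps the lower level out of everything but safety. Read that way, PK stays at planned dose and no 20 mg profile is relabelled 10 mg. The PK population wording and 16.1.1 also point to what was really taken. This stands in part: relabelling to 10 mg is one reading of an unresolved conflict, not something the SAP states outright. But 8.1 names PK explicitly, and the planned-dose reading still misplaces a profile taken after a reduction.

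A reader might also draw stronger conclusions that the documents do not support.

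- *Missed doses alone relabel a PK profile.* Six of eight 20 mg doses give 120 mg, which lies between 64 and 128. But 6/8 = 75% of administrations also meets section 9's separate provision for fewer than 80% of administrations. That provision assigns a level only for other safety analyses and is silent on PK. The dose-reduction case is the clean one.
- *Dose-normalised values are doubled.* SAP 16.1.1 calculates parameters with the administered dose, and Protocol Appendix 8 normalises by actual dose. The values are probably unaffected; only their position on the dose axis of the 16.1.2 scatter plot could be.
- *Dosing decisions were distorted.* SMC PK outputs follow a separate plan (SAP Appendix 18.1), and Cmax/Dose there uses actual dose.

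Two softening points are fair. Individual concentrations and every administration are listed (SAP 16.1.2 and 13), so a careful reader could detect a misplaced profile. And same-day dose is not a full description of a multiple-dose profile after a change, because earlier doses also contribute.

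**Conclusion.** The contradiction is real and worth correcting. SAP 8.1 and 9 assign different PK dose groups, sections 10.1 and 16.1.2 leave it open, and under either rule some profiles sit under a dose that was not given that day.

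The consequence is limited to descriptive summaries of concentrations, Cmax and AUC by dose in the study report. The 33% and 25% shifts assume dose proportionality, two or three true 10 mg participants, and that 8.1 is applied with the section 9 definition. A participant with a DLT keeps the planned dose and cannot be re-assigned. The documents do not show that anyone was affected, nor which twice-weekly cycle length was used. No hypothesis test or sample size depends on this.

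**What to change.** Reconcile SAP 8.1, 9, 10.1 and 16.1.2 with one rule:

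- PK concentrations and parameters are grouped, by regimen, by the M3258 dose administered on the day of the profile: Day 1, and whichever multiple-dose day was sampled (Day 8 or Day 15).
- Any multiple-dose profile or accumulation ratio where the dose changed or was missed beforehand carries a footnote.
- The planned/actual dose rule of section 9 does not apply to PK.

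The cost is SAP wording and one derived grouping variable. The date and dose of each administration are already recorded (Protocol 6.4) and listed (SAP 13).

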The following plots will also be provided, for key PK parameters:

- Dose Normalized C_{max} , AUC₀₋₈ and AUC_{0-tlast} for Day 1 versus Dose level as a scatter plot Any regression line should not be fixed through the origin.

For all linear PK plots, the x and y axes should both begin at (0,0).

16.2

Pharmacodynamics

The pharmacodynamic parameter analyzed are the results from the LMP7 β 5i assay and b5c assay.

Sample collection for LMP7 is on Day1 (predose, 2h, 6h and 24h and on day15 (predose, 2h and 6h). If day 15 is no longer sampled, this will be day 8. On the plate for the assay there will two wells for each sample and blank wells (sample without substrate). Before using the data, the mean of the blank wells needs to be subtracted from the mean of the two wells per treatment day and timepoint. It is assumed that this correction will already be done at the lab and only corrected values will be delivered.

The preprocessed data will be analyzed as ratio to the preprocessed baseline value ("residual activity").

If the x-axes in line plots for PD data is time, all data will be used (with respective day of analysis), analysis is not visit based.

Line plots will show the individual residual activity over time (with x-axis time, y-axis LMP7 residual activity), using different colors per regimen and per dose level and different line types to identify participants. If possible (sufficient data in a dose level), LOESS lines per regimen and per dose level can be plotted.

Summary line plots will show the mean per regimen and per dose level

Dot plots will show data of individual participants at specific selected treatment day versus dose (x-axis dose, y-axis LMP7 residual activity). Selected treatment day are:

- Day 1 24h = C1D2 predose
- Day 15 predose (If day 15 is no longer sampled, this will be day 8)

The off-target β 5c assay will be handled in the same way as the LMP7 β 5i assay, i.e. using the same plots. The expectation is to see only minimal inhibition in this assay (no changes from baseline activity to residual activity after dosing).

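### The SAP leaves LMP7 and beta-5c samples out of the dose-level summaries because of excess dosing that may have come after those samples were drawn (minor)

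*SAP*

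**What the plan says.** The rule appears three times in the main SAP. Section 7 lists it as a change from the protocol, triggered "In case the received cumulative dose is higher than planned dose". The Pd population definition in section 8.1 repeats the trigger ("In case the received cumulative dose of a participant is higher than the planned dose") and the consequence: "In summary analysis of pharmacodynamic markers the participant's data will not be included". Section 9 gives it again for the case where more than the planned dose was received: "In summary analysis of pharmacodynamic markers and efficacy analysis the data of such a participant will not be included". All three keep the participant in listings and individual-level figures, with a footnote giving the cumulative dose.

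Only section 9 gives a time window, in the line that introduces its dosing rules: "General rule for actual dose if actual dose differs from planned dose (determined during the DLT period". Protocol section 6.6 equates this with the "DLT observation period (first treatment cycle", so it is 21 or 28 days according to regimen.

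Protocol Table 5 schedules LMP7 and beta-5c on Day 1 (predose, 2 h, 6 h), Day 2 (24 h, predose) and Day 8 (predose, 2 h, 6 h) of Cycle 1. SAP 16.2 names Day 15 instead of Day 8, then adds: "If day 15 is no longer sampled, this will be day 8". It analyses each value as a ratio to baseline, handles beta-5c like LMP7, and plans mean line plots by regimen and dose level.

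**The concern.** Inclusion in a Pd summary is decided by dosing over a whole cycle, but most Pd samples fall early in that cycle. A dose taken after a sample cannot alter it. If the excess came late, the rule leaves out values that follow planned dosing exactly.

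Other parts of the SAP make the rule look out of place:

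- Section 8.1 already requires that Pd participants "have no clinically important protocol deviations or important events affecting Pd", so an overdose that really disturbs the Pd readings has a route to exclusion.
- Under section 9, a participant who received less than 80% of plan but at least 80% of a lower tested dose keeps the planned dose for every non-safety analysis. Missed doses before Day 8 therefore do not remove anyone from the Pd means, while a small excess after Day 8 does.
- The overdosed participant stays in the DLT set at the planned dose.

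At stake is how completely the mean residual-activity curves represent each dose level when cohorts are planned at 3.

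**Working it through.** The plan gives no figure to reproduce, so the check is a count of doses and samples.

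**Inputs.** Dosing days come from protocol 4.1: daily for 28 days (28 doses); twice weekly for 28 days on Days 1, 4, 8, 11, 15, 18, 22 and 25 (8 doses); daily on Days 1 to 14 of 21 (14 doses); twice weekly on Days 1, 4, 8 and 11 of 21 (4 doses). Sampling days come from protocol Table 5 and SAP 16.2. The planned cohort of 3 is from protocol 9.2.

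**Step 1: how much of the cycle lies after each sample.** Share = planned Cycle 1 doses after the sample ÷ all planned Cycle 1 doses. A dose on Day 8 or Day 15 itself is counted as not after. The Day 2 sample is predose, so only the Day 1 dose precedes it.

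| Regimen | After Day 2 predose | After Day 8 | After Day 15 |
|---|---|---|---|
| Daily, 28-day | 27/28 = 96.4% | 20/28 = 71.4% | 13/28 = 46.4% |
| Twice weekly, 28-day | 7/8 = 87.5% | 5/8 = 62.5% | 3/8 = 37.5% |
| Daily, 21-day | 13/14 = 92.9% | 6/14 = 42.9% | 0/14 = 0% |
| Twice weekly, 21-day | 3/4 = 75.0% | 1/4 = 25.0% | 0/4 = 0% |

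These shares show how much scheduled dosing follows each sample. They are not probabilities that an excess occurs.

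**Step 2: how small an excess triggers the rule.** With all other doses as planned, one extra full dose exceeds plan by 1 ÷ planned doses: 1/28 = 3.6%, 1/8 = 12.5%, 1/14 = 7.1% and 1/4 = 25%, in the order of the table. Any of these is enough. For example, 10 mg twice weekly for 28 days has a planned total of 8 × 10 = 80 mg. One extra 10 mg dose after Day 8 makes 90 mg, and every Pd value of that participant leaves the summaries, although all were drawn under planned dosing.

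**Step 3: what one exclusion removes.** Table 5 gives 3 + 1 + 3 = 7 samples per participant. The Day 1 predose value is the denominator of residual activity, so 7 − 1 = 6 outcome values remain. In a cohort of 3 that is 6 of 3 × 6 = 18, or one third. With 6 participants at a dose level it is 6 of 36, or 17%.

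**The case against.** The strongest reply is that little depends on this rule, and most of that reply stands.

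- **Dose selection.** A reader might infer that the rule distorts the choice of expansion dose, because LMP7 change serves that secondary objective and protocol 4.1 looks for a plateau over dose levels. The documents do not support this. SAP 7 records that the study stopped before Part B and before Part A met its primary objective. The separate SMC plan in SAP Appendix 18.1 has no cumulative-dose exclusion in its Pd set or Pd analyses.
- **Lost data.** It is tempting to say that valid data are thrown away. They are kept in listings, individual line plots and the dot plots of individuals against dose, which is the display closest to a plateau check.
- **Precision.** Going from 3 to 2 participants would raise a standard error by a factor of √(3/2) = 1.22. But SAP 9 reports only n, mean, minimum and maximum below 5 observations, so no planned output at that cohort size shows this.
- **Last sample on Day 8.** This holds for the current protocol only. SAP sections 5 and 16.2 name Day 15, and the protocol's amendment summary shows the move from Day 15 to Day 8. For a Day 15 sample in either 21-day regimen, no planned dose follows.
- **PK and Pd covering different people.** PK has no matching exclusion, but SAP 16.3 plans no PK/PD modelling, and section 8.1 groups PK by actual dose and Pd by planned dose. A match was never promised.
- **Bias protection.** If the excess came before a sample, leaving that sample out of a planned-dose mean is reasonable. The documents do not say when, or whether, any excess occurred, so it cannot be claimed that the rule mainly removes unaffected data.

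None of this explains why a sample drawn before the excess should be left out.

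**Conclusion.** The point holds in a limited form and is minor. The rule has no timing condition, so Pd values drawn before the first excess dose leave the mean-per-dose-level summaries without reason. This can apply to Day 1 and Day 2 values in every regimen, to Day 8 values where that day was sampled, and to Day 15 values in 28-day cycles. One such participant in a cohort of 3 costs one third of the post-baseline values at that dose level.

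The effect is confined to descriptive LMP7 and beta-5c summaries in the final report. The conclusion assumes that the section 9 window (the DLT period) also governs sections 7 and 8.1, which state none, and that at least one participant exceeded the planned cumulative dose after a Pd sample. If nobody did, the rule changes nothing. The parallel exclusion from efficacy summaries is not part of this point.

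**What to change.** In SAP 7, 8.1 and 9, keep the trigger (received cumulative dose above plan) but change its consequence for LMP7 and beta-5c. Omit from the summaries only the time points after that participant's first dose in excess of plan. Keep earlier time points under the planned dose and regimen, and footnote the omitted ones. State a convention for an excess dose on a sampling day, because the administration listing in SAP 13 gives date and dose. The wording works for Day 8 or Day 15.

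Do not replace the rule with a condition that every dose up to the sample was taken as planned. That would also remove underdosed participants, whom the SAP keeps at the planned dose for Pd, and their handling should stay as it is.

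The cost is a wording change in three places and a small programming change using administration dates and doses already collected. No new data are needed.
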